## 10.2 Unscheduled Visits

When a subject makes an unscheduled visit for adverse events etc., inquire about the reason for the visit and retain the record. The investigator will perform examinations/observations those are necessary and retain the record. If the visit is associated with any ophthalmologic symptom, identify the eye and retain the record.

If during an Unscheduled Visit the subject is discontinuing the IP or discontinuing from the study, the Investigator must conduct Exit procedures according to Table 3-1 Schedule of Study Procedures and Assessments and Section 10.1, as possible.

## **10.3 Discontinued Subjects**

### **10.3.1 Screen Failures**

Subjects who were excluded from the study after signing the informed consent, not meeting the inclusion/excursion criteria.

The Investigator must document the reason for screen failure in the subject's case history source documents.

Subject numbers must not be re-used.

### **10.3.2 Discontinuations**

The subject is discontinued in the following cases:

- 1) The investigational lens was removed for reasons of adverse events.
- 2) The investigator (or sub-investigator) judged it necessary to replace the investigational lens with another IOL.
- 3) The investigator (or sub-investigator) judged it necessary to discontinue the subject from the study.
- 4) The subject canceled the consent once issued.
- 5) The subject requested discontinuation of the study.
- 6) Continuation of the study was judged as impossible because of subject's referral or move during the study.
- 7) Other (discontinuation is necessary)

Upon discontinuation of the study, if the investigator or sub-investigator decided the examination or observation is necessary, the examination or observation should be carried out as far as possible under the subject's consent, and the date and reason of discontinuation are entered in the electric case report form. In case where continuation of the study is difficult because of discontinued visit of the subject to the clinic, the subject is followed over telephone, by mail or other appropriate means and the reason for discontinued visit, survival/death of the subject, presence/absence of adverse events, etc., are entered in the electric case report form.

If the investigational lens remained implanted in the subject after discontinuation of the study, the subject is informed as to the necessity of receiving periodical ophthalmological follow-up to assure safety at 30 – 60 days after surgery, and the subject is asked to extent cooperation as much as possible.

## **10.4 Clinical Study Termination**

If discontinuation of the entire study has become inevitable for reasons of reports on serious safety information from any participating study site or overseas, problems pertaining to the quality of the investigational lens, and so on, the Sponsor is required to immediately inform the investigator and the head of each study site of discontinuation of the study and its reason in writing.

### **10.4.1 Follow-up of subjects after study participation has ended**

[figure not shown]
Following this study, the subject will return to their eye care professional for their routine eye care.

## 11 ADVERSE EVENTS AND DEVICE DEFICIENCIES

[figure not shown]
### 11.1 General Information

An AE is any untoward medical occurrence, unintended disease or injury, or untoward clinical signs (including abnormal laboratory findings) in subjects, users, or other persons, whether or not related to the investigational medical device (test article). Refer to the Glossary of Terms and figures below for categories of AEs and SAEs.

**Figure .11-1**                      **Categorization of All Adverse Events**

**Figure .11-2**                      **Categorization of All Serious Adverse Events**

## 11.2 Procedures for Recording and Reporting

If any serious adverse event occurs, the investigator will report the type of the serious adverse event to Alcon Japan within 24 hours after confirming the event. After obtainment of detailed information on the serious adverse event, the investigator will prepare a report and immediately submit it to Alcon Japan and the head of the study sites.

All adverse events (related and unrelated to the medical device or test procedures) will be entered in the Adverse Event form. Surgically-related post-operative conditions that are normal consequences of the ocular surgery (see MOP) and not clinically relevant will be only reported as adverse events at the discretion of the investigator.

In addition, the investigator must document all serious adverse events (related and unrelated) on the Serious Adverse Event Form. Any device deficiencies will be entered in the device deficiency form within 24 hours after confirming the event.

Adverse events will also be reported for any clinically relevant change from informed consent in any protocol specific safety parameter evaluated during the study, based upon an assessment by the investigator following exposure to an investigational product.

Regarding the relationship with the investigational lens, a judgment will be made whether “not related” or “related.” Adverse events will be reported for any change in an ongoing medication and/or addition of a new medication, based upon an assessment by the investigator.

In addition, for all device deficiencies that have occurred, the details of it and the condition in which it have occurred will be entered in the device deficiency form within 24 hours after confirming the event.

Study Sponsor contact information is provided in the Manual of Procedures (MOP).

### **Causality and Intensity Assessments**

For every AE, the Investigator must assess the causality as Related or Not Related to the medical device or test procedure in the study.

### ***Causality***

- Related** An AE classified as related may be either definitely related or possibly related where a direct cause and effect relationship with the test product has not been demonstrated, but there is a reasonable possibility that the AE or device deficiency was caused by the test product.
- Not Related** An AE classified as not related may either be definitely unrelated or simply unlikely to be related (ie, there are other more likely causes for the AE).

Where appropriate, the Investigator must assess the intensity (severity) of the AE as mild, moderate, or severe, based on medical judgment with consideration of any subjective symptom(s), as defined below:

### ***Intensity (Severity)***

- Mild** An AE is mild if the subject is aware of but can easily tolerate the sign or symptom.
- Moderate** An AE is moderate if the sign or symptom results in discomfort significant enough to cause interference with the subject's usual activities.
- Severe** An AE is severe if the sign or symptom is incapacitating and results in the subject's inability to work or engage in their usual activities.

The Investigator must document any action taken (ie, medication, intervention, or treatment plan) and outcome of the AE or device deficiency when applicable.

## **11.3 Unmasking of the Study Information**

Not applicable; this study is a single treatment study.

## **11.4 Follow-Up of Safety Information**

The Investigator is responsible for adequate and safe medical care of patients during the trial and for ensuring that appropriate medical care and relevant follow-up procedures are maintained after the trial. For subjects who are experiencing ongoing unresolved adverse events at the time of their study completion or early discontinuation from the study, it is

recommended that the investigator schedule an appropriate follow-up visit in order to determine the outcome of the event.

## **11.5 Pregnancy in the Clinical Study**

If the subject becomes pregnant during the study, the investigator or sub-investigator will report it to Alcon Japan immediately. However, pregnancy is not included in adverse event. Subjects who become pregnant during the study will not be discontinued; however, all data will be excluded from the Best-Case Analysis Set (BAS).

## **12 ANALYSIS PLAN**

### **12.1 Subject Evaluability**

Final subject evaluability must be determined prior to locking the database, based upon the Deviations and Evaluability Plan.

### **12.2 Analysis Sets**

Analysis datasets used for safety and effectiveness analyses of this study are defined as follows.

#### Safety Analysis Set

The treatment-emergent safety analysis set will include all eyes with attempted implantation with the test article (successful or aborted after contact with the eye).

#### All-Implanted Analysis Set (AAS)

All-Implanted Analysis Set (AAS) will include all eyes with successful test article implantation.

#### Best-Case Analysis Set (BAS)

Best-Case Analysis Set (BAS) will include all eyes with successful test article implantation that had

- at least 1 postoperative visit;
- no macular degeneration at any time; and
- no major protocol violation

### **12.3 Demographic and Baseline Characteristics**

For all analysis datasets (Safety Analysis Set, AAS and BAS), demographics (sex, age [ $<60$ , 60-69, 70-79,  $\geq 80$ ], systemic complication [None/Yes, details] and past ocular surgery [None/Yes, details]) will be summarized with the number and percent of subjects in each category for the variable. Age will also be summarized with descriptive statistics (mean, standard deviation, number of subjects or eyes, median, min and max).

## 12.4 Effectiveness Analyses

The objective of this study is to evaluate safety and effectiveness of the investigational lens (TFNT20, T2 hereafter) when implanted to replace the natural lens following cataract removal.

### 12.4.1 Analysis of Primary Effectiveness Endpoint(s)

Primary effectiveness variables are as follows.

- Percentage of eyes with  $\leq 0.25$  D refractive cylinder at Visit 3/3A (Day 30-60)

#### 12.4.1.1 Statistical Hypotheses

The primary analysis will be performed using an exact test of binomial proportion (one-sided alpha = 2.5%). The null ( $H_0$ ) and alternative ( $H_1$ ) hypotheses are;

$$H_0: \pi(T2) = 29.2\%$$

$$H_1: \pi(T2) > 29.2\%$$

, where  $\pi(T2)$  is the population proportion of eyes with  $\leq 0.25$  D refractive cylinder at Visit 3/3A (Day 30-60) for T2 group. The 29.2% is the percentage of non-Toric (T0, hereafter) group estimated from historically combined studies [REDACTED] that would have qualified for T2 according to the new Alcon Toric calculator that incorporates ocular trends in Toric IOL planning.

#### 12.4.1.2 Analysis Methods

All eligible eyes will be used for the analysis. For unilaterally implanted subjects, only the eligible eye, for bilaterally implanted subjects, both eyes will be used for the analysis. The superiority of T2 to T0 regarding refractive cylinder is to be demonstrated when there is a statistically significant difference between the outcome in this study and the historical threshold of 29.2%.

## **12.4.2 Analysis of Secondary Effectiveness Endpoint(s)**

Secondary effectiveness variables are as follows.

[figure not shown]
- Percentage of eyes with  $\leq 0.5$  D refractive cylinder at Visit 3/3A (Day 30-60)
- Average manifest refractive cylinder at Visit 3/3A (Day 30-60)

### **12.4.2.1 Statistical Hypotheses**

No confirmative statistical hypothesis testing is planned for secondary effectiveness variables

### **12.4.2.2 Analysis Methods**

For continuous variables, descriptive statistics (mean, standard deviation, N, median, min and max) will be provided for actual value and change from baseline at each visit. For categorical variables, N and percent will be provided for each category at each visit. Any additional p-values from t-statistics or chi-square type statistics will be provided accordingly only for descriptive purpose.

## 12.5 Handling of Missing Data

No missing data will be imputed.

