Indicate whether a posterior capsulotomy was performed or not. If it was performed, report the date of the procedure and size.
- IOL observation (Visit 1/1A, Visit 2/2A and Visit 3/3A)  
Observe the IOL surface and the inside of the haptic and optic of the investigational lens with a slit-lamp microscope, and record the presence/absence of visible abnormal

findings (debris on IOL surface, forceps marks on IOL surface, IOL discoloration, IOL opacities, IOL scratch, membrane generated on IOL, pigmentation on IOL, surface haze, other.). And regarding the observed findings, evaluate the clinical significance. If the problem may negatively affect postoperative visual acuity, etc., handle it as the clinical significant, and if possible, take photos.

- IOL position change (Visit 1/1A, Visit 2/2A and Visit 3/3A)  
Tilt and/or decentration should be reported if greater than 10 degrees or 0.5mm.
- Adverse events, Device deficiencies (Visit 1/1A, Visit 2/2A and Visit 3/3A)  
Presence/absence of adverse events and device deficiencies are recorded since informed consent.
- Secondary surgical intervention (Visit 1/1A, Visit 2/2A and Visit 3/3A)  
Record the presence/absence of any postoperative surgical procedure that may be caused by the investigational lens. The SSI include iridotomy/ iridectomy for pupillary block, vitrectomy for pupillary block, adjustment of the position of the investigational lens, removal of the investigational lens due to inflammation, exchange of the investigational lens, etc., but not limited to them. Meanwhile, retinal reattachment surgery and posterior capsule resection are not included as SSI.

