2.1 Efficacy Analysis Sets

All-Implanted Analysis Set (AAS)

All-Implanted Analysis Set (AAS) will include all eyes with successful test article implantation.

Best-Case Analysis Set (BAS)

Best-Case Analysis Set (BAS) will include all eyes with successful test article implantation that had

- at least 1 postoperative visit;
- no macular degeneration at any time; and
- no major protocol violation

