4.3 Statistical Methods for Efficacy Analyses

All eligible eyes will be used for the analysis. For unilaterally implanted subjects, only the eligible eye, for bilaterally implanted subjects, both eyes will be used for the analysis. The superiority of T2 to T0 regarding refractive cylinder is to be demonstrated when there is a statistically significant difference between the outcome in this study and the historical threshold of 29.2%. [REDACTED]

Secondary effectiveness variables [REDACTED] will be summarized descriptively. For continuous variables, descriptive statistics (mean, standard deviation, N, median, min and max) will be provided for actual value and change from baseline at each visit. For categorical variables, N and percent will be provided for each category at each visit. Any additional p-values from t-statistics or chi-square type statistics will be provided accordingly only for descriptive purpose. Also, a patient data listings will be provided for all effectiveness analysis data with all eyes at all visits.

Table 4-1 summarizes the key efficacy analyses.

Table 4-1 Summary of Analysis Strategy for Key Efficacy Endpoints

[figure not shown]
Endpoint	Main [REDACTED] Approach ^a	Statistical Method	Analysis Set	Missing Data Approach
Primary				
Percentage of eyes with ≤ 0.25 D refractive cylinder at Visit 3/3A	M	Exact test of binomial proportion	AAS	Observed data only

Secondary				
Percentage of eyes with ≤ 0.5 D refractive cylinder at Visit 3/3A	M	Descriptive statistics	AAS	Observed data only

Average manifest refractive cylinder at Visit 3/3A	M	Descriptive statistics	AAS	Observed data only
--	---	------------------------	-----	--------------------

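### Observed-data-only rule lets an eye that lost the study lens leave the primary denominator instead of counting as a non-success

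*Protocol*

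**What the plan says.** The main primary analysis is an exact binomial test in the AAS. SAP 2.1 defines that set: "All-Implanted Analysis Set (AAS) will include all eyes with successful test article implantation". Table 4-1 in SAP 4.3 gives its missing-data approach as "Observed data only", and Protocol 12.5 agrees: "No missing data will be imputed".

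The protocol foresees loss of the lens. Its examples of secondary surgical intervention in 10.1.3 include "removal of the investigational lens due to inflammation, exchange of the investigational lens". Section 10.3.2 discontinues the subject when "The investigational lens was removed for reasons of adverse events" or when the investigator "judged it necessary to replace the investigational lens with another IOL".

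A Visit 3/3A refraction is not assured for such a subject. Under 10.3.2, examination at discontinuation depends on the investigator deciding that it is necessary. Under 10.2, for a discontinuation at an unscheduled visit, the investigator "must conduct Exit procedures according to Table 3-1 Schedule of Study Procedures and Assessments and Section 10.1, as possible". The 10.3.2 advice on follow-up at 30 to 60 days applies "If the investigational lens remained implanted in the subject after discontinuation of the study", so it does not reach an eye whose lens is out.

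**The concern.** An eye that loses the device has not obtained the device's result. Under the stated rule it enters neither numerator nor denominator if it has no Visit 3/3A refraction. If it is refracted in the window through a replacement lens, nothing in the visible text prevents that value from being credited to TFNT20. Compared with scoring the eye as a non-success, neither route can make the result worse for TFNT20.

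The trial is open-label and single-arm, and the comparator is a constant, so no concurrent arm loses eyes in the same way. The analysis set is named for all implanted eyes, but the percentage would describe eyes that reached Visit 3/3A, mostly with the lens in place. At about 30 eyes, one eye can matter if the count of successes falls on the boundary.

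**Working it through.** **Inputs.** Null proportion p0 = 29.2% and one-sided alpha 2.5% (Protocol 12.4.1.1, SAP 4.2). Planned proportion 60.9%, 30 eyes from 30 subjects, stated power 91.6% (Protocol 12.8, SAP 8). The documents give no removal rate, so the rates below are assumptions. Eyes are treated as independent.

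**Formula.** P(X ≥ r | n, p) = Σ from i = r to n of C(n,i) pⁱ(1−p)ⁿ⁻ⁱ. The critical value c(n) is the smallest r with P(X ≥ r | n, 0.292) ≤ 0.025.

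**The plan's own figure.** c(30) = 15, with exact alpha 0.0131. Power is P(X ≥ 15 | 30, 0.609) = 91.9%, against 91.6% stated. This is close enough to confirm the test and its inputs.

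**One removed eye.** Dropping it requires c(N−1) successes; counting it as a non-success requires c(N). For n = 29 to 40 the critical values are 14, 15, 15, 16, 16, 16, 17, 17, 17, 18, 18, 18. For N = 30 to 40 the two rules can therefore differ only at four totals, and only at one count of successes:

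| N | Eye dropped | Eye counted as non-success |
|---|---|---|
| 30 | 14/29, p = 0.0232 | 14/30, p = 0.0321 |
| 32 | 15/31, p = 0.0187 | 15/32, p = 0.0258 |
| 35 | 16/34, p = 0.0208 | 16/35, p = 0.0281 |
| 38 | 17/37, p = 0.0227 | 17/38, p = 0.0302 |

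At the other seven totals one eye cannot change the verdict.

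**Chance of disagreement at N = 30, given k removed eyes and 60.9% success among the rest.** This is P(X ≥ c(30−k)) − P(X ≥ 15), both on 30−k eyes.
- k = 1: 0.9418 − 0.8847 = 0.0571
- k = 2: 0.9142 − 0.8386 = 0.0756
- k = 3: 0.8764 − 0.7798 = 0.0966
- k = 4: 0.9086 − 0.7073 = 0.2013

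For k = 1 the figure is 14.4% at a true 50% and 1.4% at a true 29.2%.

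**Unconditional chance.** Weight these by P(k) = C(30,k) qᵏ(1−q)³⁰⁻ᵏ for an assumed per-eye removal rate q.
- q = 0.5%: 0.1297 × 0.0571 + 0.0095 × 0.0756 + smaller terms ≈ 0.8%
- q = 1%: 0.2242 × 0.0571 + 0.0328 × 0.0756 + 0.0031 × 0.0966 + smaller terms ≈ 1.6%
- q = 2%: 0.3340 × 0.0571 + 0.0988 × 0.0756 + 0.0188 × 0.0966 + 0.0026 × 0.2013 + smaller terms ≈ 2.9%

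**Type I error when only failing eyes are lost.** The true all-implanted rate is 29.2%, each failing eye is lost with probability d, and the critical value is reset to the observed n. Expected loss at N = 30 is 30 × 0.708 × d.

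| d | Eyes lost (N = 30) | Alpha, N = 30 | Same loss at random, N = 30 | Alpha range, N = 30–40 |
|---|---|---|---|---|
| 0 | 0 | 1.31% | – | 1.05–2.45% |
| 3% | 0.6 | 2.05% | 1.69% | 1.71–2.53% |
| 5% | 1.1 | 2.41% | 1.75% | 2.00–2.73% |
| 10% | 2.1 | 3.18% | 1.69% | 3.02–3.63% |

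At 3% loss alpha passes 2.5% only at N = 40, and at 5% only at N = 38 and 40. At N = 30 the crossing lies between 5% and 10%. For example, a removal rate of 5% of all eyes is 0.05/0.708 = 7.1% of failing eyes and gives 2.7%. The random-loss column shows that part of the rise at N = 30 comes from the discreteness of the test.

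**The case against.** The strongest reply is that this is a pre-specified choice, stated alike in protocol and SAP. The purpose is to assess astigmatic correction, and a lens removed for inflammation says nothing about residual cylinder, so scoring that eye as above 0.25 D assigns a result that nobody observed. Removals are reported as adverse events, and SAP 4.3 promises listings of effectiveness data for all eyes and visits, from which the alternative count can be worked out. This stands in part. The rule is neither hidden nor contradictory, and the choice is one of estimand. It does not remove the direction of the bias, and a listing does not decide which count determines success.

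The second reply also has force. The 29.2% was recalculated from earlier studies, and the visible text does not show how they handled removed lenses. If they used observed eyes only, counting removed TFNT20 eyes as failures tilts the comparison against the lens. Showing both results reveals this asymmetry but does not cure it, so the derivation of the 29.2% has to be disclosed.

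Three stronger readings are tempting but not supported:
- **That no sensitivity analysis is planned.** SAP 4.3 and the Table 4-1 header are partly redacted, no section 4.5 is visible, and the Deviations and Evaluability Plan named in Protocol 12.1 is not public. Absence cannot be claimed.
- **That the rule breaks the 2.5% error rate.** At N = 30 it does not if 3% or 5% of failing eyes are lost.
- **That the status of an exit refraction with the study lens in place is open.** The endpoint window is Day 30–60, and Protocol 10 allows examinations on separate days within the window, so an in-window value is naturally Visit 3/3A data.

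**Conclusion.** The point holds as a minor one, worth considering. On the visible text, an AAS eye that loses its study lens and has no Visit 3/3A refraction drops out of the tested percentage, and a refraction through a replacement lens is not excluded. Against a fixed threshold, the departure from a non-success rule can only favour TFNT20.

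Its size is nil if no lens is removed. Otherwise it is about a 1–3% chance of a different verdict at N = 30 and the planned 60.9%, for assumed removal rates of 0.5% to 2%. The figure of 5.7% (14.4% at a true 50%) applies only once a removal has happened. Type I error at N = 30 exceeds 2.5% only with heavier loss confined to failing eyes, such as 3.18% at 10%, which is about two eyes within 60 days.

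These figures rest on independent eyes, although both eyes of bilateral subjects are analysed, and on reading 29.2% as an all-implanted rate, which the visible text does not confirm. Unseen text may already settle the handling.

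**What to change.** In SAP 4.3 and Table 4-1, and in Protocol 12.5, state for the ≤0.25 D and ≤0.5 D endpoints:

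1. An AAS eye whose study lens is actually removed or replaced before its Visit 3/3A refraction stays in the denominator as not meeting the criterion.
2. A refraction through a replacement lens is not used.
3. Other eyes without a Visit 3/3A refraction remain under the observed-data rule, and the wholly observed-only result is reported alongside.

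Disclose whether the historical 29.2% treated removed lenses in the same way. If the hidden text does not already provide it, add a sensitivity analysis that counts every AAS eye without a Visit 3/3A refraction as a failure.

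The cost is a few sentences before database lock and no new data. The downsides are a slightly lower reported rate if a lens is removed, and possible asymmetry with the historical figure. This classifies outcomes for analysis only and leaves the management of any eye unchanged.
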